3.3.3 Demographic and Baseline Characteristics

The following demographic and baseline characteristics will be summarized:

- Age (years) and age categories (<80 years, ≥80 years)
- Sex
- Childbearing potential
- Race
- Ethnicity
- Weight (kg)
- NIHSS and NIHSS categories at baseline (6-10, >10)
- ASPECTS and ASPECTS categories (5-7, 8-10)

Demographic and baseline characteristics will be summarized with descriptive statistics or counts and percentages of subjects as appropriate by treatment and in total for each defined analysis population.

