In addition to the primary time point of each endpoint (as defined below), all other applicable time points will be compared as well and interpreted in an exploratory manner.

In these analyses, testing the combined-dose versus placebo will be done within the statistical models by averaging the results in the two active doses and comparing to placebo. (This is in contrast to performing a separate analysis in which subjects on active dose are treated as a single treatment arm.)

Generalized linear mixed models will be implemented for the analyses of disability based on mRS, infarct volume, NIHSS at 24 hours, worsening of stroke, and Barthel Index. NIHSS will be analyzed on the recorded scale of measurements and the treatment groups' Least Squares (LS) means, corresponding 95% confidence intervals (CIs), and LS mean differences will be reported. Disability based on mRS, worsening of stroke, and Barthel Index are dichotomized endpoints that will be analyzed on the logit scale of measurement. The resulting LS means and confidence intervals will be back-transformed to probabilities, and differences in least squares means will be reported as odds ratios. Infarct volume will be analyzed as log-normally distributed, and descriptive statistics will be geometric means where between-group comparisons will be reported as ratios of geometric means. Covariates baseline NIHSS and ASPECTS binary factors for efficacy analysis will use baseline values from the Electronic Data Caputre.

1. Modified Rankin Scale (mRS) score:

The effect of treatment on global disability at Day 90 will be examined by comparing the proportion of subjects who had disability (Yes or No) between the three treatments (RNS60 1.0 mL/kg/h, RNS60 0.5 mL/kg/h, and placebo 1.0 mL/kg/h) using generalized linear mixed modeling (GLM) using residual pseudo-likelihood with a subject-specific expansion(RSPL) assuming a binary outcome (0-2=0, 3-6=1). Covariates include the Age, baseline NIHSS, and ASPECTS binary factors used for block urn randomization and baseline (pre-morbid) mRS, baseline occlusion location, study site, baseline perfusion status, and log of baseline infarct volume. Treatment, visit day, and interaction of treatment and visit day are included as categorical fixed effects.

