The dataset generated in Step 3 (which contains monotone missing data) will be imputed based on the assumption of MNAR, using Copy-Reference imputation. The MNAR imputation will be based on trajectories in the placebo group, i.e., data from the placebo group only will be used to generate the imputations. This step will include data for active subjects identified in step 3 along with all placebo subjects. For this, the MNAR statement will be used as described below.

Step 5: Analysis of imputed data with GLM

The imputed datasets generated in Step 4 do contain only non-missing values and are used as input in the statistical model. The final step before statistical inference is to convert the imputed mRS data (on the 0-6) scale to the binary endpoint (0-2, 3-6). Residual pseudo-likelihood with a subject-specific expansion (RSPL) based GLMs will be run on each of the 500 generated imputed datasets. For additional details on how to specify the GLM, see the analysis section corresponding with this sensitivity analysis.

Step 6: Combination of results from the GLMs

Finally, the MIANALYZE procedure in SAS will be applied to combine the 500 results from the analyses generated in Step 4, to derive an estimate of the treatment difference at day 90. In addition to the estimate, corresponding two-sided 95% CIs and p-values will be generated with the MIANALYZE procedure.

2. Volume of stroke or Infarct volume (Diffusion-weighted imaging, DWI):

Infarct progression/regression will be analyzed as measured by MRI brain imaging. Where MRI was not available, infarct volumes will be obtained from a 48-hour CT imaging. Infarct volume will

be summarized with descriptive statistics at Baseline, 24 hour, 48 hour, and Day 90 timepoints. The volume difference between 48 hour and 24 hour and between Day 90 and 24 hour timepoint will also be summarized.

The simple effect of treatment on Infarct progression/regression will be examined by 48-hour infarct volume on a log scale between the three treatments (RNS60 1.0 mL/kg/h, RNS60 0.5 mL/kg/h, and placebo 1.0 mL/kg/h) using GLM using maximum likelihood assuming a Gaussian distribution. Covariates include the log of baseline infarct volume along with Age, baseline NIHSS, ASPECTS binary factors used for block urn randomization, baseline perfusion status, baseline occlusion location, and study site.

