Additionally, neurological functioning at Day 90 will be examined by NIHSS scores at Day 90 between the three treatments (RNS60 1.0 mL/kg/h, RNS60 0.5 mL/kg/h, and placebo 1.0 mL/kg/h). GLM analysis and missing data imputation analysis at Day 90 will be performed using the same approach described above for neurological functioning using 24-hour NIHSS scores.

4. The proportion of subjects with worsening of stroke over the 48-hours/duration of admission:

Worsening of stroke is defined (i.e., Yes or No) as: progression, or hemorrhagic transformation, of the index stroke as documented by medical imaging and that is (a) life-threatening requiring intervention and/or (b) results in increased disability as gauged by a \geq 4-point increase from lowest NIHSS pre decline and/or (c) results in death. Subjects with worsening of stroke will be identified based on a \geq 4-point increase in their worst minus best NIHSS score and adverse events status (life threatening requiring intervention or death) as collected in the CRFs.

The simple effect of treatment on worsening stroke at 48 hours/admission duration will be examined by comparing the proportion of subjects who had worsening stroke (Yes or No) between the three treatments (RNS60 1.0 mL/kg/h, RNS60 0.5 mL/kg/h, and placebo 1.0 mL/kg/h) using GLM using residual pseudo-likelihood with a subject-specific expansion (RSPL) assuming a binary distribution. Covariates include the Age, baseline NIHSS, and baseline ASPECTS as binary factors used for block urn randomization, log of baseline infarct volume, baseline perfusion status, baseline occlusion location, and study site.

The predicted probability for each treatment group and LS mean difference between high-dose and placebo and low-dose and placebo groups along with the 95% CIs will be provided using the LSMEANS/DIFF statement. The comparison of the two combined active arms versus placebo will be performed using the LSMESTIMATE statement with the ILINK option. The odds ratio will also be calculated. The P-value for the hypothesis testing will also be provided. Treatment difference will be assessed with a 2-sided alpha level of 0.05.

The sample SAS code planned for the analysis is outlined below.

5. Barthel Index.

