The effect of treatment on functional independence at Day 90 will be examined by comparing subjects achieving functional independence (Barthel Index score ≥ 95 as compared to < 95) where subjects having a score ≥ 95 on the Barthel Index Score at Day 90 will be deemed to have achieved functional independence, and those scoring < 95 at Day 90 will be deemed to have failed to achieve functional independence.

The proportion of subjects who achieved functional independence (BI score ≥ 95 vs. < 95) at Day 90 will be compared between the three treatments (RNS60 1.0 mL/kg/h, RNS60 0.5 mL/kg/h, and placebo 1.0 mL/kg/h) using generalized linear mixed modeling using RSPL assuming a binary outcome ($< 95 = 0$, $\geq 95 = 1$). Covariates include the Age, baseline NIHSS, and ASPECTS binary factors used for block urn randomization and baseline BI total, log of baseline infarct volume, baseline perfusion status, baseline occlusion location, and study site. Treatment, visit day, and interaction of treatment and visit day are included as categorical fixed effects.

Sensitivity analysis of BI will be performed in a similar way to the primary analysis using the GLM approach with RSPL assuming a binary outcome ($<95=0$, $\geq 95=1$) where any missing value of BI will be imputed as functional independence not achieved (coded as 0).

3.4.3 Sensitivity Analysis for Secondary Efficacy Endpoints with Dichotomous Data for Baseline Collaterals

For each of the secondary efficacy endpoints described in section 3.4.2, additional sensitivity analysis will be performed using the GLM analysis approach where baseline collaterals will also be included in the model. For subjects with a baseline collateral score, the score will be converted to baseline collateral status. Baseline collaterals dichotomization will use the following conversion approach:

Dichotomization A (main): where a baseline collateral score of 0-2 indicates Baseline collateral status = Absent, and a baseline collateral score of 3-5 indicates Baseline collateral status = Present

Dichotomization B: where a baseline collateral score of 0 indicates Baseline collateral status = Absent, and a baseline collateral score of 1-5 indicates Baseline collateral status = Present.

Dichotomization C: where a baseline collateral score of 0-1 indicates Baseline collateral status = Absent, and a baseline collateral score of 2-5 indicates Baseline collateral status = Present.

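### Four efficacy models use age, baseline NIHSS and ASPECTS only as two-level factors, giving up prognostic information and a little power that linear terms would recover

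*SAP*

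**What the plan says.** SAP 3.4.2 gives the covariates endpoint by endpoint.

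- mRS (1): "Covariates include the Age, baseline NIHSS, and ASPECTS binary factors used for block urn randomization", plus pre-morbid mRS, occlusion location, site, perfusion status and log baseline infarct volume.
- Infarct volume (2): "Covariates include the log of baseline infarct volume along with Age, baseline NIHSS, ASPECTS binary factors used for block urn randomization", plus perfusion status, occlusion location and site.
- Worsening of stroke (4): "Covariates include the Age, baseline NIHSS, and baseline ASPECTS as binary factors used for block urn randomization", plus log baseline infarct volume, perfusion status, occlusion location and site.
- Barthel Index (5): "Covariates include the Age, baseline NIHSS, and ASPECTS binary factors used for block urn randomization and baseline BI total, log of baseline infarct volume", plus perfusion status, occlusion location and site.

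A general sentence in the same section adds: "Covariates baseline NIHSS and ASPECTS binary factors for efficacy analysis will use baseline values from the Electronic Data Caputre". The cuts are age 80, NIHSS 6-10 against above 10, and ASPECTS 5-7 against 8-10 (SAP 2.2.1). SAP 3.3.3 summarises all three variables both on their full scale and in categories, so the full values exist.

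No planned sensitivity model uses the full scale. SAP 3.4.3 adds collaterals, and SAP 3.4.4.3 mentions time since last known well and thrombolytics. The covariate list for the 24-hour NIHSS model cannot be read in the public text, so that model is not counted here.

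**The concern.** A two-level factor treats everyone on the same side of the cut as having the same prognosis. The NIHSS cut is the clearest case. Under inclusion criterion 4 of the protocol, patients with M2 occlusion must already score above 10, so only ICA and M1 patients can fall in 6-10. The other level runs from 11 to 42.

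What is at stake is efficiency. The target is 100 patients in three equal arms (100/3, about 33 per arm), no power analysis was done (SAP 2.2.4), and Protocol 9.3.3 says the efficacy results are meant to supply effect sizes for a later trial. A linear term takes one parameter, as a two-level factor does, so the information could be used without a larger model. The same models already carry other baseline measures on a full scale, namely log infarct volume and the Barthel total.

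**Working it through.** The plan gives no figure for information lost, no covariate distributions and no assumed effects. Everything below that depends on these is an assumption shown over a range.

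**Step 1. Information kept by a split.** For a covariate with a linear effect, the share kept is the squared correlation between the covariate and its split. For a normal covariate with share p in the smaller level this is φ(z_p)² / [p(1−p)].

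- p = 0.50: 0.637 kept, 36% lost
- p = 0.25: 0.539 kept, 46% lost
- p = 0.20: 0.490 kept, 51% lost
- p = 0.10: 0.342 kept, 66% lost

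The loss equals one half at p = 0.209.

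**Step 2. The three covariates.** Five assumed distributions were tried for each. Age and NIHSS were truncated normal (age mean 65-75, SD 12-13; NIHSS mean 12-18, SD 5-6). ASPECTS was computed exactly on 5-10.

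| Covariate | Share in the named level | Loss |
|---|---|---|
| Age, 80 or over | 33% down to 12% | 41% to 63% |
| NIHSS, 6-10 | 32% down to 9% | 45% to 72% |
| ASPECTS, 5-7 | 50% down to 10% | 23% to 40% |

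So the loss is roughly a quarter to two-thirds, with 72% the extreme. It was half or more in four of five cases for NIHSS, in three of five for age, and in none for ASPECTS.

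**Step 3. The Gaussian model (infarct volume).** With no other covariates, the variance ratio of split to linear is [1 − R²(1−L)] / (1 − R²), with L the share lost. At R² = 0.2 and L = 0.5 it is 0.9/0.8 = 1.125. That overstates the cost here, because log baseline volume is already in the model and only the partial correlation matters.

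Take assumed correlations of outcome with baseline volume 0.9, outcome with NIHSS 0.5 and NIHSS with baseline volume 0.4.

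- Linear NIHSS: partial r = (0.5 − 0.36)/√(0.19 × 0.84) = 0.350, squared 0.123.
- An 80/20 split multiplies both NIHSS correlations by √0.49 = 0.7: partial r = (0.35 − 0.252)/√(0.19 × 0.9216) = 0.234, squared 0.055.
- Ratio: (1 − 0.055)/(1 − 0.123) = 0.945/0.877 = 1.08.

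Over correlations of 0.7-0.9, 0.4-0.5 and 0.4-0.5 respectively, the penalty is 0% to 8%.

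**Step 4. The binary mRS endpoint.** Logistic regression was simulated with 33 per arm, two-sided 0.05, a single visit, no site effect and 1,500 replicates. Assumed inputs: age mean 70, SD 13; NIHSS mean 16, SD 6; logit effects 0.6 per 13 years, 0.7 per 6 NIHSS points, −0.3 per 1.4 ASPECTS points and 0.5 per unit of log infarct volume.

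| True OR | Infarct volume in model | Split | Linear |
|---|---|---|---|
| 1 | yes | 5.5% | 5.5% |
| 0.4 | yes | 31.7% | 33.7% |
| 0.25 | yes | 59.6% | 62.5% |
| 0.4 | no | 29.7% | 32.6% |
| 0.25 | no | 56.8% | 62.1% |

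The Monte Carlo SE is about 1.3 points per figure. Both models were fitted to the same simulated trials, so the differences are less noisy than that.

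A second set of assumptions (85% with NIHSS above 10, 22% aged 80 or over, 0.08-0.15 logit per NIHSS point, 0.03-0.05 per year, no infarct volume) moved power at OR 3 from 51/47/42% to 53/51/47%, and at OR 4 from 69/64/61% to 71/68/67%. Further runs at OR 3 gave changes of −1 to +5 points without infarct volume and +1 to +3 with it.

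**Step 5. Standard error of the log odds ratio.** At OR 3 without infarct volume (3,000 trials per setting), moving from split to linear raised the median SE from 0.559 to 0.575, 0.563 to 0.594 and 0.566 to 0.614. The ratios are 1.03, 1.06 and 1.08. Power still rose by 2 to 5 points, because the conditional odds ratio lies further from 1 when finer covariates are held fixed.

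**The case against.** Adjusting for the factors used in randomization is a recognised and principled choice, and SAP 3.4.2 gives that reason for its imputation models. Replacing the factors with linear terms takes the strata out of the main model, and keeping both would cost three parameters in a model that is already heavily adjusted. Linearity on the logit scale is assumed without support from the documents. The endpoints are secondary in an unpowered safety trial, and the gain is a few power points at large assumed odds ratios.

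Much of this stands, and it limits the point to a modest improvement. Two things weaken the strata argument. The SAP already loosens the match to the randomization by taking NIHSS and ASPECTS from the data capture system, and a retained binary-factor analysis shows the as-stratified result. The other covariates do recover part of the loss. However, the infarct volume called baseline comes from an MRI about 2 hours after thrombectomy (SAP 3.1.3), whereas infusion starts before arterial access closure. It is therefore not a pre-treatment measure in the way that age, NIHSS and ASPECTS are.

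A reader might infer three stronger things that the documents do not support.

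- That half or more of the information is lost for all three covariates. This depends on undocumented shares and did not occur for ASPECTS.
- That linear terms would narrow the interval for the mRS odds ratio. In simulation the interval widened slightly.
- That chance imbalance within the NIHSS above 10 level is a separate bias. Under randomization it is the mechanism of the efficiency loss, not a second harm.

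**Conclusion.** The point holds as a cheap, modest improvement. Four models use only the two-level versions although full values are recorded and linear terms need no more parameters. Roughly a quarter to two-thirds of each covariate's linear prognostic information is given up, most plausibly half or more for NIHSS.

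For the treatment comparison, the expected gain in the binary mRS analysis is about 1 to 3 power points with infarct volume in the model. Without it the gain is up to about 5, or 6 in the single most favourable setting. Type I error was unchanged. In the infarct volume model the variance penalty of an 80/20 NIHSS split is about 0% to 8%.

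These sizes rest on assumed distributions, linear effects, assumed correlations and a simplified single-visit model. The planned analysis remains valid; it is only somewhat less efficient than it could be.

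**What to change.** Before unblinding, amend SAP 3.4.2 (1), (2), (4) and (5) so that age in years, baseline NIHSS in points and ASPECTS (5-10) enter as linear covariates in place of the two-level factors. Keep the binary-factor models as sensitivity analyses. Use the same form in the imputation models if their code, which is blacked out in the public copy, uses the binary factors. State the covariate form for the 24-hour and Day 90 NIHSS models in the same way.

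Reconcile the NIHSS cut as well. Protocol 4.1 and SAP 2.2.1 use 6-10 against above 10, while Protocol 4.2 uses below 10 against 10 or more. The linear term does not depend on this, but the sensitivity analysis does.

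The cost is SAP wording and about one line of code per model, with no added parameters. The downsides are an assumption of roughly linear effects and an odds ratio that is conditional on finer covariates. The report should say the latter wherever the estimate is used to plan the next trial.

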10.2.2 Imaging

At baseline all participants will undergo NCCT and CTA (with mCTA preferred) imaging for assessment of inclusion into the trial. If mCTA is not standard of care at the imaging facility, single phase CTA (CTA) can be used to confirm intracranial occlusion eligibility. If CTA is not available, CTP may be used. To evaluate for the presence or absence of collaterals, mCTA, single phase CTA or CTP can be utilized. The immediate post-thrombectomy (within approximately 2 hours) and 48-h MRI will be used to assess perfusion imaging and infarct volume and will include a minimum of axial DWI, gradient-echo (GRE), FLAIR, T2, and 3D T1 weighted dataset). The 48-h MR is considered a standard of care imaging procedure. If any MRI cannot be obtained (due to subject compliance or limitations) a CT will be performed.

The baseline NCCT and CTA and all brain/neurovascular imaging conducted up to the Day 90 MR will be rendered anonymous and sent to the central core imaging lab. The core imaging lab staff will review the imaging as per an Imaging Charter in order to ensure adherence to the imaging guidelines and enrollment criteria for training purposes. The core imaging lab will confirm determination of baseline ASPECT scores, as well as reperfusion rates (TICI scores) and infarct growth from immediately after thrombectomy to 48h. In addition, overall injury to the

affected hemisphere will be compared between groups by comparing volume loss/gliosis between the 90-d and post-thrombectomy MRI.

For all interval times assessed from imaging, the time zero will be the first slice of the NCCT scan. Imaging date and time will be collected in the CRF.

Notes:

The use of a dynamic CTA or multiphase CTA data acquisition protocol is preferred. Baseline NCCT and CTA may be completed at a hospital affiliated with the trial site.

10.3 Appendix 4: Adverse Events: Definitions and Procedures for Recording, Evaluating, Follow-up, and Reporting

AE Definition

An AE is any untoward medical occurrence in a patient or clinical investigation participant administered a pharmaceutical product and which does not necessarily have to have a causal relationship with this treatment.
 
An AE can therefore be any unfavorable and unintended sign (including an abnormal laboratory finding, for example), symptom or disease temporally associated with the use of a medicinal product, whether or not considered related to the medicinal product.

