The attributes of the main estimand (target of estimation), used for the primary analysis of the highest ranked efficacy endpoint (modified Rankin Scale (mRS) score) are defined below. Although the primary objective of this study is related to safety, analysis of the efficacy endpoints (secondary objectives of the study) will be based on a pre-defined hierarchy and therefore, an estimand is defined.

- The **population** is defined as the intent-to-treat study population (see Section 3.2.3).
- The corresponding **variable** to be obtained for each subject required to address the scientific question is disability based on the mRS score at Day 90. The mRS will be evaluated as a binary outcome (0-2, 3-6).
- The **population level summary** considered in this study is the odds ratio between RNS60 1.0 mL/kg/h and placebo 1.0 mL/kg/h.
- The **treatments** to be compared are RNS60 1.0 mL/kg/h and placebo 1.0 mL/kg/h. The treatments will be compared according to the randomized groups, regardless of the treatment that was actually received. In accordance with the treatment policy principle, all available data will be used in the analysis, regardless of e.g., premature discontinuation of study medication or administration of any concomitant treatment.
- The **intercurrent events** (ICEs) considered as potentially impacting results and/or interpretation are:
 - Premature discontinuation of study treatment
 - Death
 - Coronavirus Disease 2019 (COVID-19) pandemic related events (assessments that were missed due to COVID-19).

For the data that are missing due to premature discontinuation of study treatment, an assumption of Missing At Random (MAR) will be made. Sensitivity analyses will be conducted using an assumption of Missing Not At Random (MNAR). No specific imputation will be done for these missing data, because the likelihood-based analysis approach can manage subjects with incomplete data under the assumption of MAR.

For the data that are missing due to COVID-19, an assumption of MAR will be made for all analyses, both primary and sensitivity analyses.

For the mRS, NIHSS and BI endpoints death is included as part of the scoring, so no imputation of these endpoints is required for subjects who die. Similarly, for the worsening of stroke endpoint, death represents a worsening. For the infarct progression end point, death will be represented by a missing value.

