3 STATISTICAL METHODOLOGY

3.1 General Considerations

3.1.1 *Analysis Day*

Analysis days will be calculated from the date of starting infusion of study drug. The day on which infusion of study drug is started is Day 1, and the day immediately before Day 1 is Day -1. For the purpose of this statistical analysis there is no Day 0.

3.1.2 *Analysis Visits*

Scheduled visits will be assigned to analysis visits as recorded on the case report form (CRF). Unscheduled and early termination visits will be assigned to analysis visits according to the analysis windows in Table 5. The record occurring on the target day will be picked for the time point analysis. If the record on a target day does not exist, then the one closest to the target date will be used.

Table 5. Analysis windows

| Analysis Visit | Target Analysis Day | Low Analysis Day | High Analysis Day |
|----------------|---------------------|------------------|-------------------|
| Baseline | -1 | | -1 |
| DAY 1 | 1 | 1 | 1 |
| DAY 2 | 2 | 2 | 3 |
| DAY 6 | 6 | 4 | 8 |
| DAY 30 | 30 | 9 | 44 |
| DAY 90 | 90 | 45 | 104 |

3.1.3 *Definition of Baseline*

Baseline is defined as the last measurement prior to start of the study drug infusion. Baseline blood work, ECG and CXR (Day 1) are not required prior to randomization or start of study drug infusion. Baseline infarct volume indicates the initial infarct volume as obtained from the first MRI approximately 2 hours post-endovascular thrombectomy on Day 1.

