3.1.6 Handling of Dropouts and Missing Data

For participants who have missing observations on 90-day mRS, 24-hour NIHSS, worsening stroke, or infarct volume, the missing data in the primary analyses will be managed with an assumption of MAR using longitudinal mixed models. In addition, every effort will be made to complete assessments using the participants legally authorized representative (LAR) for information if needed. Assessments with missing elements will be considered missing as a whole. Missing dates will be queried at the site level prior to database lock.

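### The main mRS model needs an MRI-only post-thrombectomy infarct volume and the SAP gives no rule for a missing value, so patients with an observed Day 90 mRS would be omitted

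*SAP*

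**What the plan says.** **Estimand.** SAP 2.1.3 sets a treatment-policy estimand for Day 90 mRS (0-2 versus 3-6) and states that "all available data will be used in the analysis, regardless of e.g., premature discontinuation of study medication". Deaths score 6 (SAP 3.1.7).

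**Model.** The covariates in SAP 3.4.2(1) include "baseline (pre-morbid) mRS, baseline occlusion location, study site, baseline perfusion status, and log of baseline infarct volume". The worsening model in 3.4.2(4) and the Barthel model in 3.4.2(5) also list log baseline infarct volume.

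**Definition of the covariate.** SAP 3.1.3: "Baseline infarct volume indicates the initial infarct volume as obtained from the first MRI approximately 2 hours post-endovascular thrombectomy on Day 1".

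**CT as a fallback.** Protocol 10.2.2: "If any MRI cannot be obtained (due to subject compliance or limitations) a CT will be performed". SAP 3.4.2(2), under the infarct endpoint: "Where MRI was not available, infarct volumes will be obtained from a 48-hour CT imaging".

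**Missing data.** SAP 3.1.6 lists mRS, NIHSS, worsening and infarct volume, and says that "the missing data in the primary analyses will be managed with an assumption of MAR using longitudinal mixed models". For outcomes missing after early discontinuation of treatment, SAP 2.1.3 adds: "No specific imputation will be done for these missing data, because the likelihood-based analysis approach can manage subjects with incomplete data".

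**Sensitivity analysis.** The MNAR analysis of mRS imputes the mRS, with age, NIHSS and ASPECTS named as factors, and then fits the same model. Step 5 says: "The imputed datasets generated in Step 4 do contain only non-missing values and are used as input in the statistical model". The SAS code is blacked out in the public SAP.

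**The concern.** Taken together, the MRI-only definition, the covariate list and the absence of imputation mean that a patient without the early MRI has no value for a required covariate. Such a patient cannot enter the fit, however complete the mRS follow-up.

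The exclusion would arise after randomization and after dosing has begun. It is also plausibly related to outcome, because patients who are unstable, or who die, before a scan due about 2 hours after the procedure are not a random subset. Disability at Day 90 ranks first in the efficacy hierarchy, and the efficacy results are meant to inform the powering of a later trial (Protocol 9.3.3). At stake are the match between analysis and estimand, precision in arms of about 33, and the modelled disability rates. The odds ratio is also at stake if the arms differ in who is omitted.

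**Working it through.** **1. Does the stated method cover this case?** SAP 3.4.3 names PROC GLIMMIX as the procedure used in 3.4.2. A mixed model under MAR uses a patient's observed visits when other visits are missing. It puts no distribution on the covariates, so a record without the covariate has no linear predictor. Infarct volume appears in SAP 3.1.6 as an endpoint, and the mRS model does not model it. The volume is one value per patient, so its absence removes every mRS visit for that patient.

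**2. Does a CT fill the gap?** Protocol 10.2.2 applies to any MRI, so a CT should exist for a missed post-thrombectomy MRI. SAP 3.1.3 does not admit it as the baseline volume. The CT in SAP 3.4.2(2) is the 48-hour one, and using that as baseline would contradict 3.1.3.

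**3. How large could the effect be?** The plan has no power calculation or MRI failure rate, so there is no stated figure to reproduce. Inputs:
- N = 100, 1:1:1, so n = 33.3 per arm (SAP 2.2.1 and 2.2.4).
- Disability (mRS 3-6) 50%, because Protocol 2.1 says about half reach independence.
- Assumed: share unscanned m = 5%, 10% or 20%; share of these disabled q = 70% or 80%.

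Analysed disability rate = (0.50 − m·q)/(1 − m). Unadjusted 95% CI factor for an odds ratio at 50% in both arms = exp(1.96·√(8/n)), with n = 33.3·(1 − m).

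| m | q = 70% | q = 80% | Patients left | n per arm | CI factor |
|---|---|---|---|---|---|
| 0 | 50.0% | 50.0% | 100 | 33.3 | 2.61 |
| 5% | 0.465/0.95 = 48.9% | 0.460/0.95 = 48.4% | 95 | 31.7 | 2.68 |
| 10% | 0.430/0.90 = 47.8% | 0.420/0.90 = 46.7% | 90 | 30.0 | 2.75 |
| 20% | 0.360/0.80 = 45.0% | 0.340/0.80 = 42.5% | 80 | 26.7 | 2.93 |

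**4. When does the odds ratio move?** Analysed OR = true OR × (a₁/a₀)/(p₁/p₀). Here a and p are the shares retained on active and placebo, with subscript 1 for independent and 0 for disabled patients. If retention given outcome is the same in both arms, the factor is 1 and the odds ratio is unchanged.

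Differential example: independence 50% on placebo and 60% on active (OR 1.5), 15% and 5% unscanned, and 20% of the unscanned independent.
- Placebo: (0.50 − 0.15·0.20)/0.85 = 0.47/0.85 = 0.553; odds 0.47/0.38 = 1.237.
- Active: (0.60 − 0.05·0.20)/0.95 = 0.59/0.95 = 0.621; odds 0.59/0.36 = 1.639.
- Analysed OR = 1.639/1.237 = 1.325. ln 1.325/ln 1.5 = 0.281/0.405 = 0.69, so about 31% of the log odds ratio is lost.

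The bias can also run the other way. With no true effect, 50% disabled in each arm, 90% of the unscanned disabled, and 10% versus 20% unscanned, the odds of disability are 0.41/0.49 = 0.837 and 0.32/0.48 = 0.667. Their ratio is 0.80, in favour of the arm with more unscanned patients.

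**The case against.** The strongest reply is that no sentence in either document says these patients are dropped. Three stronger readings are tempting, and the documents do not support them.

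- *There is no substitute for the missing MRI.* The protocol obtains a CT. What is missing is a SAP statement that its volume may serve as the baseline covariate.
- *The Step 5 statement is untrue for this covariate.* This cannot be verified. The mRS text names only age, NIHSS and ASPECTS, but the infarct-volume analysis names the same three and also mentions log-transforming baseline volume before imputation. The three-factor sentence is therefore not a full list of imputation variables, and the code is not readable.
- *The treatment effect would be biased as a matter of course.* It would not, as step 4 shows. The example of 15% versus 5% is about 5 versus 2 patients per arm, a strong assumption for a scan about 2 hours after the procedure. The figures are also unadjusted, and missingness explained by age, NIHSS, ASPECTS, occlusion site or pre-morbid mRS need not bias the conditional odds ratio.

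There are mitigations. Protocol 5.2 excludes foreseeable inability to have MRI, so only unforeseen failures count. The Day 90 mRS counts, percentages and bar graphs, and the Wilcoxon tests in SAP 3.4.4.1, do not need the volume and would keep these patients. Efficacy is secondary in a trial with no power calculation.

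All of this limits the size of the problem. It does not close the gap, because the analysis attached to the estimand is the covariate-adjusted model, and its main fit is described without imputation.

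**Conclusion.** The concern holds as a conflict within the SAP. As written, the main mRS model, and likewise the worsening and Barthel models, would omit patients with an unforeseen missed post-thrombectomy MRI even when the outcome is known, including deaths. That contradicts the estimand's commitment on available data. Omission is the consequence of the stated model and not a written rule. Whether the MNAR code repairs it in the sensitivity analysis is unknown.

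Size rests on assumptions. With 5-20% unscanned and 70-80% of them disabled, the analysed disability rate is about 49% to 43% against a true 50%, and 5 to 20 of 100 patients are lost. An odds ratio of 1.5 falls to about 1.33 only under a marked arm difference (15% versus 5%). The gap should be closed before database lock. It does not touch the primary safety analysis.

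**What to change.** 1. In SAP 3.1.3, accept the volume from the post-thrombectomy CT when the first MRI was not done. Carry this into 3.4.2(1), (4) and (5).
2. Where neither scan gives a volume, impute the log baseline volume under MAR before fitting these models, within the multiple-imputation framework already planned, so that every ITT patient with an observed outcome is analysed. State in the mRS sensitivity analysis that this covariate is among the imputed variables.
3. Add a sensitivity analysis of the same three models without the volume covariate. It also covers patients who died before any scan, for whom an imputed volume is only a device to retain the outcome.
4. Report, per arm, how many patients have a CT-based or an imputed baseline volume.

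The cost is SAP wording and minor code, with no new data collection. The downside is some measurement difference between CT and MRI volumes, which items 3 and 4 make visible. Removing the covariate from the main models would also close the gap, but it gives up prognostic adjustment and is more debatable.
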